7.3. Severity of TEAEs/SAEs

The severity (mild, moderate, or severe) of each TEAE/SAE must be assessed by the Investigator, or designee. The following criteria should be considered when assessing severity:

- Mild The symptom is barely noticeable to the patient and does not influence performance or functioning.
- Moderate The symptom is of sufficient severity to make the patient uncomfortable, and performance of daily activities is influenced. Treatment for the symptom may be needed.
- Severe The symptom causes severe discomfort. Treatment for the symptom may be necessary.

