7.4. Assessment of Relatedness to Study Drug or Device

The Investigator will assess each TEAE and ADE for causality based on their medical judgment and the observed symptoms associated with the event. Each TEAE and ADE will be assessed as related or unrelated to study drug based on the following criteria:

- Unrelated This category applies to those TEAEs and ADEs that the Investigator determines are most likely due to extraneous causes (disease, environment, etc.) and does not follow a reasonable temporal relationship.
- Related This category applies to those TEAEs and ADEs that the Investigator determines are most likely due to test drug or device.

7.5. Method, Frequency, and Time Period for Detecting Adverse Events and Serious Adverse Events

At appropriate intervals (e.g., at every study visit and telephone contact), patients should be assessed for TEAEs and SAEs. After the patient has had an opportunity to spontaneously mention any problems, the Investigator should inquire about TEAEs by asking a non-leading question such as the following:

1. “How are you feeling?”
2. “Have you had any medical problems since your last assessment/visit?”
3. “Have you taken any new medicines since your last assessment/visit?”

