4.2. SAFETY ENDPOINTS

Safety endpoints are as follows:

- Incidence of treatment-emergent drug/device-related adverse events
- Changes from Baseline to Month 2/Study Termination in clinical laboratory and vital signs*

* Changes from Baseline to Month 2 and Month 4 will be summarized. In the absence of data at the relevant visit early termination data may be used if collected within the visit window (see Section 6.4).

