6. GENERAL ASPECTS FOR STATISTICAL ANALYSIS

6.1. GENERAL METHODS

Subjects differ by treatment history prior to entry to Study LTI-301 - the two groups will be referred to as the Transition and Add-On Groups. For all summary tables data will be presented for all subjects (Overall) and by group.

Continuous variables will be summarized using the number of non-missing observations (n), mean, standard deviation (SD), standard error (SE), median, minimum and maximum. Categorical variables will be summarized using frequencies and percentages.

Categorical shift tables will include marginal totals.

Unless otherwise specified, the estimated mean and median for a set of values should be printed out to 1 more decimal place than the original values, and SD and SE should be printed out to 2 more decimal places than the original values. The minimum and maximum should report the same number of decimal places as the original values.

Percentages will be displayed with 1 decimal place; except percentages will not be presented when the count is zero and 100% will be presented as an integer. The number of subjects in the analysis population will be the denominator.

Unless stated otherwise, baseline will be taken as the last available non-missing assessment prior to study drug administration (Day 1).

In by-visit summary tables, the baseline will be summarized using all available data, but also for each visit using only the baseline data from subjects with available data at the visit; hence the mean change from baseline will equal the mean visit value – mean baseline value.

Throughout this document ‘change from baseline’ refers to the actual change from baseline (i.e. visit value – baseline value).

All data will be listed separately for each group. Data listings will present study days in addition to dates, where study day is derived as (assessment date – first day of dosing + 1).

Since there is no formal hypothesis testing, no adjustment for multiplicity will be made for inferential statistical comparisons within or between groups.

Programming of analyses, tables and listings will be performed using R Version 3.4.0 or higher (R Foundation for Statistical Computing, Vienna, Austria) or SAS® Version 9.3 or higher (Cary, North Carolina, US).

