6.2.2. ADVERSE EVENT CLASSIFICATIONS

AEs with missing classifications will be assumed to be the following:

- missing causality will be taken as treatment related
- missing seriousness will be taken as serious
- missing severity will be taken as severe

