8.1. ADVERSE EVENTS

AEs will be coded using MedDRA version 20.1.

AEs will be considered TEAE unless there is clear indication that the event occurred prior to the first dose of study drug. AEs present prior to study drug administration that increased in severity or relationship to study drug afterwards will also be classed as TEAEs.

All AEs that occur after the first dose of study drug will be considered to be 'treatment-

'emergent' with the exception of AEs that occur more than 7 days after the last dose of study drug.

Events with missing or partial dates will be handled such that in the absence of contradictory information an AE is treatment emergent (see Section 6.2).

Only TEAEs will be included in the summary tables.

An overall summary will present the number of subjects with:

- any TEAE*
- any TEAE considered as related to study drug (evaluated by the investigator as Related or severity not reported)*
- any serious TEAE*
- any serious TEAE considered as related to study drug*
- Maximum severity TEAEs of mild, moderate or severe; i.e. a subject with TEAEs at different intensities will be summarized at the most severe intensity
- Maximum severity TEAEs considered as related to study drug of mild, moderate or severe; i.e. a subject with TEAEs at different intensities will be summarized at the most severe intensity
- any TEAE leading to study drug discontinuation (i.e. TEAEs reported as having either an action taken as 'Drug Withdrawn') and/or Study Discontinuation*
- any TEAE considered as related study drug discontinuation (i.e. TEAEs reported as having either an action taken as 'Drug Withdrawn') and/or Study Discontinuation *
- any TEAE leading to death*

The table will also include the total number of TEAEs reported for those flagged (*). The total number of unique terms within subjects will also be presented for those flagged (*), counting each TEAE PT only once within each subject.

This overall summary will be presented for both the Safety and mITT populations.

This summary will also be produced using the Safety population for the following:

- the subgroups in Section 6.3
- those TEAEs with an onset up to the Month 2 visit (inclusive) and those with an onset after the Month 2 visit separately.

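### SAP 8.1 defines a drug-related TEAE partly by missing severity, where SAP 6.2.2 uses missing causality; the related-TEAE count then depends on an order of imputation that the SAP does not state

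*SAP*

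**What the plan says.** SAP 6.2.2 gives a general rule for incomplete adverse-event records: "AEs with missing classifications will be assumed to be the following". It has three separate parts. Two matter here: "missing causality will be taken as treatment related" and "missing severity will be taken as severe". The third deals with seriousness.

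SAP 8.1 then lists the rows of the overall TEAE summary. The drug-related row is "any TEAE considered as related to study drug (evaluated by the investigator as Related or severity not reported". It does not mention missing causality. No other related row in that list (serious related, related by maximum severity, related leading to discontinuation) has a definition of its own, and neither do the related SOC/PT summaries later in 8.1.

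The protocol treats the two attributes as separate assessments. On severity, section 7.3 says: "The severity (mild, moderate, or severe) of each TEAE/SAE must be assessed by the Investigator, or designee". On causality, section 7.4 says: "Each TEAE and ADE will be assessed as related or unrelated to study drug based on the following criteria".

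The count feeds a named safety endpoint in SAP 4.2: "Incidence of treatment-emergent drug/device-related adverse events".

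**The concern.** Severity and causality are different fields, and nothing else in either document makes an absent severity grade a reason to call an event drug-related. The clause in 8.1 reads like a slip in which severity was written for causality. Taken literally, it gives one table row a rule that differs from 6.2.2.

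Two things are at stake. One is the count of subjects with a drug-related TEAE, for which two rules in the same plan can give two answers. The other is consistency within the table: the neighbouring related rows have no parenthesis and would fall back on 6.2.2, so rows that should reconcile might not. The affected row is one of those flagged to show subjects, total events and unique terms. The summary is produced for the Safety and mITT populations and, in the Safety population, for the subgroups and for onset up to and after the Month 2 visit. Any discrepancy would be repeated across those outputs.

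**Working it through.** The plan gives no figure to reproduce, since this is a classification rule. The check crosses causality (Related, Unrelated, missing) with severity (reported, missing), giving 3 × 2 = 6 cells, and asks whether each reading counts the event as related.

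- **Reading A:** 8.1 on unimputed data, with the parenthesis as the complete definition.
- **Reading B:** 8.1 on unimputed severity, with 6.2.2 still supplying the answer for missing causality.
- **Reading C:** all 6.2.2 imputations made before 8.1 is applied.

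| Causality | Severity | 6.2.2 | A | B | C |
|---|---|---|---|---|---|
| Related | reported | yes | yes | yes | yes |
| Related | missing | yes | yes | yes | yes |
| Unrelated | reported | no | no | no | no |
| Unrelated | missing | no | **yes** | **yes** | no |
| Missing | reported | yes | **no** | yes | yes |
| Missing | missing | yes | yes | yes | yes |

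Reading A agrees with 6.2.2 in 4 of 6 cells. Its two conflicts run in opposite directions: it over-counts Unrelated events with missing severity and under-counts events with missing causality and reported severity. Reading B agrees in 5 of 6 and only over-counts. Reading C agrees in 6 of 6. With causality in place of severity in the parenthesis, the literal rule also agrees in 6 of 6, whatever the order.

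**Reconciliation between rows.** Suppose a subject's only TEAE is Unrelated with missing severity. Under A or B the subject enters the any-related row. If the related maximum-severity rows follow 6.2.2, the subject is in none of them. Under A the reverse holds for a subject whose only TEAE has missing causality and reported severity: absent from the any-related row, but present in one of the related severity rows.

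**Size per subject.** The denominators are the Safety Population counts in SAP 5.2:

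- Overall: 1/121 = 0.83%, about 0.8 percentage points
- Transition: 1/55 = 1.82%, about 1.8 points
- Add-On: 1/66 = 1.52%, about 1.5 points

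The row counts subjects with any related TEAE, so a subject changes category only if the misclassified event decides that status. A subject with another event that is counted as related either way stays in the row. The number of events with missing severity or causality is not given, so the net change cannot be calculated.

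**The case against.** The strongest reply is that 6.2.2 already settles the matter. It is written as a general rule for adverse events, and its natural use is when the analysis dataset is derived. Severity is then never missing, missing causality is already related, and the stray clause selects nothing. This is a fair reading, and under it the table is correct. What remains is that the SAP does not state the order. The reference in 8.1 back to section 6.2 concerns missing or partial dates, and the parenthesis itself describes data as reported, before imputation. A programmer who follows 8.1 literally is still following the plan.

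A second reply is that the under-count is the weaker half. SAP 8.1 never says that events with missing causality are unrelated. It is silent, and 6.2.2 answers the case expressly. This stands: the under-count needs the parenthesis to be read as exhaustive and severity to be reported. The over-count is the only place where 8.1 affirmatively gives a wrong instruction.

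A third reply is that the triggering records should be rare. The protocol requires severity and causality for each event (7.3, 7.4), insists on causality in initial SAE reports (7.6.3), and has monitors check eCRF completeness (9.3.1). This also stands, and the number of affected events may be zero.

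A reader might infer that the two rules will necessarily produce two different counts, or that each misclassified event shifts the rate. The documents support neither. A difference needs a missing field and a program that does not apply 6.2.2 beforehand, and the rate moves only when the event decides the subject's status.

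**Conclusion.** The textual conflict is certain; an effect on reported results is conditional. SAP 8.1 names the wrong attribute in its definition of a drug-related TEAE. Programmed on unimputed data, it would count some Unrelated events as related and, on the exhaustive reading, would also drop the conservative default that 6.2.2 sets for events without a causality assessment.

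The effect is probably small, on the assumption that few records lack either field. Its net direction is unknown, because the two errors can offset. The per-subject shifts shown above apply only where the misclassified event is decisive.

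It would be tempting to say that the primary safety result is compromised. The documents do not support that. The primary endpoint in SAP 4.1 is the incidence of TEAEs and SAEs regardless of causality, and its reference to relationship concerns dose titration. No formal hypothesis test depends on the row either (Protocol 8.4). The reach is the drug-related safety endpoint and the internal consistency of its tables. The point should be corrected because the error is clear and the repair is nearly free; it does not threaten the study's conclusions.

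**What to change.** In the drug-related bullet of SAP 8.1, replace the word severity with causality inside the parenthesis, or delete the parenthesis and refer to 6.2.2. Add one sentence stating that the 6.2.2 imputations are made before any related-TEAE row of the overall summary and the related SOC/PT summaries are derived, so that all of them share one definition.

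The cost is one word and one sentence, with no new data and no new analysis. SAP section 2 allows amendments before database lock. After lock, the definition and order actually used should be documented in the clinical study report. Reporting how many TEAEs had missing causality or missing severity would show whether the point had any effect.

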¹Prescribed Tyvaso Dose is the dose on which the patient has been stable in concordance with the study eligibility criteria.

Day 1

1. PK samplings will be collected over a 4 hour period after administration of the final Tyvaso dose. LIQ861 should be administered at the appropriate starting dose beginning with the second dose on Day 1.
 - a. If the starting dose of LIQ861 is not tolerated, the next dose of LIQ861 may be decreased by 25 µg treprostinil strength.
 - b. If the starting dose does not appear to be providing similar efficacy to the patient's Tyvaso treatment, the next dose of LIQ861 may be increased by 25 µg and the patient should be observed for at least an hour after the increase prior to discharge from the clinic at the Investigator's discretion.

Day 2

1. For the first dose on Day 2, LIQ861 should be administered at the same dose as the last tolerated dose taken on Day 1, and PK samples should be collected over a 4 hour period. After completion of the PK sampling, the patient may be discharged at the discretion of the Investigator.
2. At the Week 2 Visit, or after 2 weeks of QID administration of LIQ861, if the patient is experiencing sufficient symptomatic relief AND is tolerating the treatment, that dose should be maintained unless symptoms worsen.
 - b. If the patient is not experiencing sufficient symptomatic relief OR is not tolerating the treatment, LIQ861 may be increased or decreased by 25 µg treprostinil strength increments, respectively.
3. Additional dosing increases may be implemented at 25 µg increments per week up to a maximum of 150 µg. Prior to any dose titration the Investigator should contact the patient by

phone to assess degree of symptomatic relief and tolerance and need/desire to adjust the LIQ861 dose.

Management of Side Effects

If symptoms of PGI₂ excess are observed, further dose increases of LIQ861 should be avoided until these symptoms subside.

If side effects cannot be tolerated or medically managed, one or more of the following strategies may be employed:

- Reduction of LIQ861 in 25 µg treprostinil strength increments until symptoms subside
- Discontinuation of LIQ861

Employment of any of the above strategies for mitigation of non-tolerated side effects should be documented in the eCRFs.

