3. STUDY OVERVIEW

3.1. STUDY OBJECTIVES

The primary objective of this study is to evaluate the long-term safety and tolerability of LIQ861 in patients with PAH.

The secondary objective of this study is to evaluate the comparative bioavailability of treprostинil between two formulations of inhaled therapy.

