7.5. EXTENT OF EXPOSURE

The duration of treatment will be summarized as both a continuous variable using descriptive statistics and as a categorical variable (e.g., <2 months, 2 to <4months, 4 to <8 months..). Duration of treatment is defined as (date of last dose – date of first dose +1). The duration will be summarized for each dose and overall.

For these summaries a month will be taken to be 28 days in duration.

At Months 2, 4 and 8 (Study Days 56, 112 and 224) the average daily dose (mcg) will be summarized. Summaries will be generated for all subjects who had the potential to reach the visit (taking dose as 0 for those who have withdrawn prior to the visit) and for all subjects

still ongoing in the study at the visit.

Dose shifts from baseline will also be presented by visit.

The number and percentage of Transition subjects with sustained transition treatment through the end of Month 2 will be tabulated by initial dose and overall, where sustained transition treatment is defined as:

- treatment with LIQ861 through at least 2 months beyond transition from Tyvaso
- no interruptions to study treatment totaling more than 7 days prior to the end of Month 2
- no treatment with any prostacyclin or prostacyclin analogs apart from administration of LIQ861

The number and percentage of subjects on each dose of LIQ861 will also be tabulated against the previous Tyvaso dose for Transition subjects at Months 2, 4, 8 and 12.

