The number and percentage of subjects with TEAEs will be presented by system organ class (SOC) and PT for both the Safety and mITT populations. Subjects with multiple TEAEs within a SOC or SOC/PT combination will be counted only once for that SOC or SOC/PT combination.

A similar summary will be presented for the Safety population of TEAEs considered as study drug related.

The 'all causality' summary will also be produced using the Safety population for the following:

- the subgroups in Section 6.3
- those TEAEs with an onset up to the Month 2 visit (inclusive) and those with an onset after the Month 2 visit separately.

SOC and PT summaries of TEAEs by maximum severity (mild, moderate or severe) will be presented for all TEAEs and also for those considered as related to study drug.

All summaries will be ordered by descending frequency of total number of subjects within each SOC and then similarly by decreasing frequency of total number of subjects within each PT, in the overall column. In cases of SOCs or PTs with equal frequencies, AEs will be sorted alphabetically.

All TEAEs will be listed by subject and AE onset day. AE duration (stop date/time – start date/time) will be included in the listing; where applicable imputed data will be used for the calculation of AE duration, but the original date information will be presented in the listing.

The following separate listings will also be provided:

- serious AEs
- TEAEs leading to study drug discontinuation (i.e. TEAEs reported as having either an action taken as 'Drug Withdrawn') and/or Study Discontinuation

If there are any deaths a listing will include the date of death and the adverse event(s) associated with death.

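### By action taken, SAP 8.1 summarises only TEAEs that lead to discontinuation; TEAE-driven dose reductions and interruptions are not summarised

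*SAP*

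**What the plan says.** SAP 3.1 sets the aim: "The primary objective of this study is to evaluate the long-term safety and tolerability of LIQ861 in patients with PAH".

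Protocol Appendix 2, under management of side effects, gives two strategies for effects that are neither tolerable nor medically manageable. One is reduction in 25 µg "treprostinil strength increments until symptoms subside"; the other is stopping LIQ861. It adds: "Employment of any of the above strategies for mitigation of non-tolerated side effects should be documented in the eCRFs".

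SAP 8.1 classifies TEAEs by their effect on treatment in one way only. The overall summary has a row for "any TEAE leading to study drug discontinuation" and a matching row for related events. The separate listing covers "TEAEs leading to study drug discontinuation (i.e. TEAEs reported as having either an action taken as 'Drug Withdrawn') and/or Study Discontinuation". There is no row or listing for reduction or interruption.

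SAP 8.1 does count events whatever the action taken: "The number and percentage of subjects with TEAEs will be presented by system organ class (SOC) and PT for both the Safety and mITT populations". It also summarises related and serious TEAEs, maximum severity and TEAEs leading to death.

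Dose data appear in SAP 7.5. It covers duration at each dose, average daily dose at Months 2, 4 and 8, LIQ861 dose against prior Tyvaso dose for Transition subjects, and a shift table: "Dose shifts from baseline will also be presented by visit". SAP 7.5 also makes the absence of interruptions adding up to over 7 days before the end of Month 2 one of three conditions for sustained transition. SAP 7.6 adjusts the number of dosing days in the compliance rate for interruptions caused by AEs.

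**The concern.** When each patient's dose is adjusted individually, stopping the drug is only the extreme end of intolerance. A patient whose dose is cut, or who pauses treatment because of a TEAE and then continues, has also met a treatment-limiting effect. The protocol anticipates this and asks for it to be documented, but the SAP has no table that reports it.

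At stake is how fully the final report can answer the tolerability half of the primary objective. A reader could see how many patients had each event, how severe it was, and how many stopped because of one. The reader could not see how many stayed on treatment only after a reduction or pause.

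**Working it through.** The plan states no figure on this point, so there is none to reproduce. The check asks whether any planned output identifies a TEAE-driven reduction or interruption.

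1. **Overall TEAE summary and SOC/PT tables (SAP 8.1).** These count the event, but the only consequences for the patient that they show are discontinuation and death. The all-TEAE listing specifies onset day and duration and does not mention action taken.

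2. **Dose shifts (SAP 7.5).** No reason for a change is attached. The section does not define the baseline dose; assume it is the starting dose. Add-On patients start at 25 mcg (SAP 3.5), the lowest capsule strength. For a patient raised to peak P and then cut by one 25 mcg step, net shift = (P − 25) − 25:
   - P = 50: 0
   - P = 75: +25
   - P = 100: +50
   - P = 125: +75
   - P = 150: +100

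   The shift in per-dose strength is never negative. Add-On patients are 66 of the 121 in the Safety Population (SAP 5.2): 66/121 = 54.5%. For the 55 Transition patients, who start between 25 and 150 µg (Protocol Appendix 2, Table 2), a cut below the starting dose would show as a decrease, but with no cause given.

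3. **Average daily dose (SAP 7.5).** This is a group summary at three time points. Upward and downward changes are averaged together and are not linked to AEs.

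4. **Sustained transition (SAP 7.5).** It covers Transition patients only, to Month 2 only, and only interruptions totalling more than 7 days, whatever the cause. Add-On patients and all later follow-up fall outside it, and SAP Version 2.0 is the plan for final reporting.

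5. **Compliance (SAP 7.6).** Rate = 100% × capsules taken / capsules that should have been taken. Let D be the days from first to last dose, d the days interrupted for an AE, and k the capsules per day, held constant. If AE interruption days are removed from the dosing days, as the wording suggests, a patient who takes everything outside the pause has 100% × k(D − d) / k(D − d) = 100%. The interruption disappears from the result.

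6. **Grouping by relation to dose titration (SAP 4.1).** This is named in the primary endpoint but has no table in SAP 8.1.

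7. **Direction.** Let A be the number of patients with a TEAE leading to discontinuation, and U the number with a TEAE-driven reduction or interruption who are not in A. Treatment-limiting TEAEs affect (A + U)/121; the plan reports A/121. Since U ≥ 0, the reported figure equals or understates the total, by U/121.

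8. **What an added row would show.** The documents give neither A nor U. With assumed counts and N = 121, exact (Clopper-Pearson) 95% intervals are:
   - 6/121: 1.8% to 10.5%
   - 12/121: 5.2% to 16.7%
   - 24/121: 13.1% to 28.1%
   - 36/121: 21.8% to 38.7%

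   These show the precision available, not an expected rate.

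**The case against.** The best defence is that the primary endpoint is the incidence of TEAEs and SAEs, not discontinuation. A patient whose dose was cut for an event is counted with that event, by SOC/PT, severity and relatedness. The study is descriptive, with no formal testing, and nothing in either document says that tolerability will be judged on discontinuation alone. This stands. A reader might infer that the SAP counts only TEAEs leading to discontinuation, that patients with a dose cut will look tolerant, or that the tolerability conclusion is biased. The documents do not support any of these. What is missing is the treatment consequence, not the event.

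The dose outputs also give a partial, unattributed picture, and SAP 6.1 says all data will be listed, so patient-level review may be possible. This also stands, but it leaves readers to reconstruct a count that the report could state.

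Appendix 2 names reduction and discontinuation but not interruption. That is correct; the case for an interruption row rests on SAP 7.6.

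Neither document promises these tables, and recording data does not oblige the sponsor to tabulate them. That too is correct: this is a gap in reporting against the objective, not a broken commitment or an invalid method.

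Finally, the eCRF is not shown. The only action-taken value visible is drug withdrawal, and Appendix 2 does not say that a reduction is recorded against an event. The fix has to allow for that.

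**Conclusion.** The point holds as a reporting gap that is worth closing. By action taken, SAP 8.1 summarises and separately lists discontinuation only, and no other planned summary attributes a dose reduction or interruption to a TEAE. Used as the measure of treatment-limiting intolerance, discontinuation can only equal or understate it.

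The size is unknown. Any multiplier of the discontinuation rate would merely restate assumed counts, so none is offered.

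The conclusion that the shift table cannot show a decrease for Add-On patients assumes that baseline means the starting dose and that shifts are in per-dose strength. The compliance result assumes that AE interruption days are removed from the dosing days. The main finding needs neither assumption, because none of these outputs is linked to AEs under any reading.

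**What to change.** Add three rows to the SAP 8.1 overall summary: any TEAE leading to dose reduction; any TEAE leading to dose interruption; and any TEAE leading to reduction, interruption or discontinuation. Give each for all TEAEs and for related TEAEs, by group and overall, with the Safety Population as denominator. Add a matching listing beside the existing discontinuation listing.

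State the data source. Use the AE action-taken field if it has these categories. If not, use the eCRF dose-change and interruption records matched to AEs, with the matching rule written down before the tables are run.

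The cost is a few rows, one listing and possibly some record matching. SAP Section 2 allows amendment before database lock; after that, the rows can be documented in the CSR as an additional analysis. The change concerns reporting only and proposes no dosing rule.
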